## **11.6 Study documentation, record keeping and retention of documents**

Each participating site will maintain appropriate medical and research records for this trial, in compliance with Section 4.9 of the ICH E6 GCP, and regulatory and institutional requirements for the protection of confidentiality of subjects. As part of participating in a Novartis-sponsored study, each site will permit authorized representatives of the sponsor(s) and regulatory agencies to examine (and when required by applicable law, to copy) clinical records for the purposes of quality assurance reviews, audits and evaluation of the study safety and progress.

Source data are all information, original records of clinical findings, observations, or other activities in a clinical trial necessary for the reconstruction and evaluation of the trial. Examples of these original documents and data records include, but are not limited to, hospital records, clinical and office charts, laboratory notes, memoranda, subjects' diaries or evaluation checklists, pharmacy dispensing records, recorded data from automated instruments, copies or transcriptions certified after verification as being accurate and complete, microfiches, photographic negatives, microfilm or magnetic media, x-rays, and subject files and records kept at the pharmacy, at the laboratories, and medico-technical departments involved in the clinical trial.

Data collection is the responsibility of the clinical trial staff at the site under the supervision of the site Principal Investigator. The study case report form (CRF) is the primary data collection instrument for the study. The investigator should ensure the accuracy, completeness, legibility, and timeliness of the data reported in the CRFs and all other required reports. Data reported on the CRF, that are derived from source documents, should be consistent with the source documents or the discrepancies should be explained. All data requested on the CRF must be recorded. Any missing data must be explained. Any change or correction to a paper CRF should be dated, initialed, and explained (if necessary) and should not obscure the original entry. For electronic CRFs an audit trail will be maintained by the system. The investigator should retain records of the changes and corrections to paper CRFs.

The investigator/institution should maintain the trial documents as specified in Essential Documents for the Conduct of a Clinical Trial (ICH E6 Section 8) and as required by applicable regulations and/or guidelines. The investigator/institution should take measures to prevent accidental or premature destruction of these documents.

Essential documents (written and electronic) should be retained for a period of not less than fifteen (15) years from the completion of the Clinical Trial unless Sponsor provides written permission to dispose of them or, requires their retention for an additional period of time because of applicable laws, regulations and/or guidelines.

### **11.7 Confidentiality of study documents and patient records**

The investigator must ensure anonymity of the patients; patients must not be identified by names in any documents submitted to Novartis. Signed informed consent forms and patient enrollment log must be kept strictly confidential to enable patient identification at the site.

### **11.8 Audits and inspections**

Source data/documents must be available to inspections by Novartis or designee or Health Authorities.

### **11.9 Financial disclosures**

Financial disclosures should be provided by study personnel who are directly involved in the treatment or evaluation of patients at the site - prior to study start.

## **12 Protocol adherence**

Investigators ascertain they will apply due diligence to avoid protocol deviations. Under no circumstances should the investigator contact Novartis or its agents, if any, monitoring the study to request approval of a protocol deviation, as no authorized deviations are permitted. If the investigator feels a protocol deviation would improve the conduct of the study this must be considered a protocol amendment, and unless such an amendment is agreed upon by Novartis and approved by the IRB/IEC/REB it cannot be implemented. All significant protocol deviations will be recorded and reported in the CSR.

### **12.1 Amendments to the protocol**

Any change or addition to the protocol can only be made in a written protocol amendment that must be approved by Novartis, Health Authorities where required, and the IRB/IEC/REB. Only amendments that are required for patient safety may be implemented prior to IRB/IEC/REB approval. Notwithstanding the need for approval of formal protocol amendments, the investigator is expected to take any immediate action required for the safety of any patient included in this study, even if this action represents a deviation from the protocol. In such cases, Novartis should be notified of this action and the IRB/IEC at the study site should be informed according to local regulations (e.g. UK requires the notification of urgent safety measures within 3 days) but not later than 10 working days.

**Document History – Changes compared to previous version of SAP**

---

Version	Date	Changes
1.0	08Nov2013	Final version
2.0	07Feb2020	To update the SAP per protocol amendment 1 

• To change the primary endpoint from number of patients receiving everolimus to frequency and severity of AEs/SAEs to better characterize the long-term safety of the compound

• To include the collection of all AEs (including non-serious AEs) and an investigator attestation of continued clinical benefit. In addition, SAP is also updated to follow Novartis SAP template.

	09Jun2020	To update the SAP on the basis of amendment 1 and the change of safety data collection in protocol amendment 1 

• Safety data from both ARGUS safety database and RDC clinical database will be analyzed separately for comprehensive and transparent safety data reporting in final CSR.

• To include global protocol amendment date 18-Mar-2016 as a general cutoff date to analyze safety data from RDC clinical database.

---

## List of abbreviations

AE	Adverse event
AESI	Adverse events of special interest
BSC	Best Supportive Care
CRF	Case Report/Record Form; the term CRF can be applied to either EDC or Paper
CRO	Contract Research Organization
CSP	Clinical Study Protocol
CSR	Clinical Study Report
CTCAE	Common Terminology Criteria for Adverse Events
EC	European Commission
eCRS	Electronic Case Retrieval Strategy
IB	Investigator's Brochure
ICH	International Conference on Harmonization
IEC	Independent Ethics Committee
IIT	Investigator-initiated Trial
IRB	Institutional Review Board
OGD&GMA	Oncology Global Development and Global Medical Affairs
PI	Principal Investigator
PT	Preffered Term
REB	Research Ethics Board
SAE	Serious Adverse Event
SAP	Statistical Analysis Plan
SOC	System Organ Class
SOP	Standard Operating Procedure

## **1 Introduction**

This document provides the detailed statistical analysis plan (SAP) for the data from study CRAD001C2X01B. Data analysis will be performed by Novartis personnel or a designated third party.

The original RAP Module 3 for study CRAD001C2X01B was finalized in November 2013 after the initial protocol was released. Subsequently clinical study protocol (CSP) amendment 1 was released in March 2016 to change the primary endpoint from number of patients receiving everolimus to frequency and severity of AEs/SAEs to better characterize the long-term safety of the compound. In addition, the CSP has been amended to include the collection of all AEs (including non-serious AEs) and an investigator attestation of continued clinical benefit. This SAP amendment is to incorporate the impact of CSP amendment 1 on the analysis.

### **1.1 Study design**

[figure not shown]
This is a multi-center, open label study to better characterize the long-term safety of everolimus in patients currently being treated in a Novartis-sponsored Oncology Global Development and Global Medical Affairs (OGD&GMA) study and who are not progressing on the current study treatment as judged by the investigator.

Parent studies eligible to participate in the roll-over study will be decided by Novartis. Investigator initiated trials (IIT) will not be included. The primary objective of the parent study must have been reached and the parent study must be in the process of being completed and reported. Patients may be allowed to continue combination therapy with Sandostatin LAR® Depot if they are currently receiving this combination therapy on the parent protocol and at the discretion of the investigator.

Patients will continue to be treated in the roll-over protocol until they are no longer benefiting from their everolimus treatment as judged by the investigator (disease progression), they develop unacceptable toxicities, they withdraw consent, they are non-compliant to the protocol, the investigator feels it is no longer in the patient's best interest to continue everolimus therapy or the patient dies, whichever comes first. At every quarterly visit, the investigator is required to confirm that the patient continues to have clinical benefit and may continue receiving study treatment. A patient will reach the end of study when everolimus treatment is permanently discontinued.

The study is expected to remain open until such time that enrolled patients no longer need treatment with everolimus or are able to obtain commercial supply according to local regulations for their medical condition.

**Figure 1-1 Study design**

\*Note: The starting everolimus (and Sandostatin LAR® Depot, if applicable) dose will be the same as the last dose received in the parent study.

## 1.2 Study objectives and endpoints

Objectives and related endpoints are described in Table 1-1 below.

**Table 1-1 Objectives and related endpoints**

Objective	Endpoint	Analysis
Primary		
To evaluate long term safety data	Frequency and severity of AEs/SAEs	Refer to Section 2.5 & 2.8
Secondary		
To evaluate clinical benefit as assessed by the investigator	Proportion of patients with clinical benefit as assessed by the investigator at scheduled visits	Refer to Section 2.7

## **2 Statistical methods**

### **2.1 Data analysis general information**

Data will be analyzed by Novartis using SAS Version 9.3. Only data reported in the database of this protocol will be included in the analyses. Patient data from the parent study will not be taken into account.

Summary tables will be provided for patient disposition, demographic data and treatment exposure. All data collected on the database will be listed, using all patients enrolled in this study.

Categorical data will be presented as frequencies and percentages. For continuous data, mean, standard deviation, median, minimum, and maximum will be presented, unless otherwise stated.

The original protocol was released on 07-Dec-2012. Protocol amendment 1 (PA1) was released on 18-Mar-2016. In this amendment the primary endpoint was changed to safety to better characterize the long-term safety of the compound. In addition, the protocol has been amended to include the collection of all AEs (including non-serious AEs) and an investigator attestation of continued clinical benefit. Additional eCRFs were added to collect data related to

- Investigator attestation of clinical benefit at every quarterly visit
- All adverse events (based on original protocol only SAEs were collected and all SAEs were only collected in ARGUS safety database)
- Relevant medical history/current medical conditions
- Monthly at home pregnancy testing for female patients of child bearing potential (serum/urine)
- Study evaluation completion at the end of the 30 day safety follow up
- Related imaging, drug use 6 months prior to liver event, pathology, medical history possibly contributing to liver dysfunction, local laboratory results (viral serology, autoimmune, immunoglobulin, liver function tests), overview, potential impact of alcohol use, acetaminophen/paracetamol pertaining to liver event (only when drug-induced liver injury (DILI) cases occur)

However, at the time of global protocol amendment was released, 32 out of 34 patients were enrolled; 21 patients ongoing; 11 patients had already discontinued the study. Only 2 patients consented after PA1 approval. Therefore, 32/34 patients did not have AEs collected in eCRFs before PA1, ~30% of enrolled patients had AEs reported in RDC clinical database after PA1, and ~50% of SAEs occurred before PA1 were not reported in RDC. Due to this, safety data from both ARGUS safety database and RDC clinical database will be analyzed separately for comprehensive and transparent safety data reporting in final CSR. See section 2.8.2 in detail.

### **2.1.1 General definitions**

**Study drug** = RAD001 = everolimus = Afinitor®.

**Study treatment** is defined as everolimus or everolimus + Sandostatin LAR if patients are allowed to continue combination therapy.

**Date of first administration of study drug** is defined as the first date when a nonzero dose of study drug was administered and recorded on eCRF. For the sake of simplicity, the date of first administration of study drug will also be referred as start of study drug.

**Date of last administration of study drug** is defined as the last date when a nonzero dose of study drug was administered and recorded on the database of this protocol.

The date of first and last administration of sandostatin LAR is defined in the same way.

**Date of first administration of study treatment** is defined as the first date when a nonzero dose of study treatment was administered and recorded on the database of this protocol.

**Date of last administration of study treatment** is defined as the last date when a nonzero dose of study drug was administered and recorded on the database of this protocol.

**Study day** is calculated as: date of the event (onset date of an event, assessment date...) – first date of the first administration of study treatment + 1. Therefore, the first day of study treatment is study day 1.

**Baseline** is defined when appropriate as the the non-missing record with the latest assessment date on or before the date of first administration of study treatment.

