Study treatment	Includes any drug or combination of drugs in any study arm administered to the patient (subject) as part of the required study procedures, including placebo and active drug run-ins. In specific examples, it is important to judge investigational treatment component relationship relative to a study treatment combination; study treatment in this case refers to the investigational and non-investigational treatments in combination.
Study treatment discontinuation	Point/time when patient permanently stops taking study treatment for any reason
Supportive treatment	Refers to any treatment required by the exposure to a study treatment, e.g. premedication of vitamin supplementation and corticosteroid for pemetrexed disodium.
Treatment group	A treatment group defines the dose and regimen or the combination, and may consist of 1 or more cohorts. Cohorts are not expanded, new cohorts are enrolled.

Variable	Identifier used in the data analysis; derived directly or indirectly from data collected using specified assessments at specified timepoints
Withdrawal of consent	Withdrawal of consent occurs only when a patient does not want to participate in the study any longer, and does not want any further visits or assessments, and does not want any further study related contact

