## 6 Treatment

### 6.1 Study treatment

Study treatment and investigational treatment refer to everolimus.

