**Table 6-2 Combination therapy dose and treatment schedule**

Study treatments	Pharmaceutical form and route of administration	Dose	Frequency and/or Regimen
[Redacted content]			

Study treatments	Pharmaceutical form and route of administration	Dose	Frequency and/or Regimen
Sandostatin LAR® (if applicable)	Intramuscular injection	At discretion of treating physician	At discretion of treating physician

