3. Its relationship to the study treatment (reasonable possibility that AE is related: No, Yes)
4. Action taken with respect to study or investigational treatment (none, dose adjusted, temporarily interrupted, permanently discontinued, unknown, not applicable)
5. Whether medication or therapy was given (no concomitant medication/non-drug therapy, concomitant medication/non-drug therapy)
6. Whether it is serious, where a serious adverse event (SAE) is defined as in Section 8.2.1

If the event worsens the event should be reported a second time in the CRF noting the start date when the event worsens in toxicity. For grade 3 and 4 adverse events only, if improvement to a lower grade is determined a new entry for this event should be reported in the CRF noting the start date when the event improved from having been Grade 3 or Grade 4.

All adverse events should be treated appropriately. If a concomitant medication or non-drug therapy is given, this action should be recorded on the Adverse Event CRF.

Once an adverse event is detected, it should be followed until its resolution or until it is judged to be permanent, and assessment should be made at each visit (or more frequently, if necessary) of any changes in severity, the suspected relationship to the study treatment, the interventions required to treat it, and the outcome.

Progression of malignancy (including fatal outcomes), if documented by use of appropriate method (for example, as per RECIST criteria for solid tumors or as per Cheson's guidelines for hematological malignancies), should not be reported as a serious adverse event.

Adverse events separate from the progression of malignancy (example, deep vein thrombosis at the time of progression or hemoptysis concurrent with finding of disease progression) will be reported as per usual guidelines used for such events with proper attribution regarding relatedness to the drug.

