Information about all SAEs is collected and recorded on the Serious Adverse Event Report Form; all applicable sections of the form must be completed in order to provide a clinically thorough report. The investigator must assess and record the relationship of each SAE to each specific study treatment (if there is more than one study treatment), complete the SAE Report Form in English, and submit the completed form within 24 hours to Novartis. Detailed instructions regarding the SAE submission process and requirements for signatures are to be found in the investigator folder provided to each site.

Follow-up information is submitted in the same way as the original SAE Report. Each re-occurrence, complication, or progression of the original event should be reported as a follow-up to that event regardless of when it occurs. The follow-up information should describe whether the event has resolved or continues, if and how it was treated, whether the blind was broken or not, and whether the patient continued or withdrew from study participation.

If the SAE is not previously documented in the Investigator's Brochure or Package Insert (new occurrence) and is thought to be related to the Novartis study treatment, an oncology Novartis Drug Safety and Epidemiology (DS&E) department associate may urgently require further information from the investigator for Health Authority reporting. Novartis may need to issue an Investigator Notification (IN), to inform all investigators involved in any study with the same drug that this SAE has been reported. Suspected Unexpected Serious Adverse Reactions (SUSARs) will be collected and reported to the competent authorities and relevant ethics committees in accordance with Directive 2001/20/EC or as per national regulatory requirements in participating countries.

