### 2.8.2 Adverse events (AEs)

Verbatim terms will be coded to lower-level terms in the Medical Dictionary for Regulatory Activities (MedDRA). AEs will be coded to MedDRA. An assessment of severity grade will be made using NCI-CTCAE v4.03. Summary tables for adverse events (AEs) will include only AEs that started or worsened during the on-treatment period, the *treatment-emergent* AEs. The incidence of treatment-emergent adverse events (new or worsening from baseline) will be summarized by System Organ Class (SOC) and or Preferred Term (PT), severity (CTC Grade 1-4, 5 Death is excluded), type of adverse event, relation to study treatment.

Since safety data collection was changed in the protocol amendment released on 18-Mar-2016, CTC grade were captured in the RDC clinical database only after the protocol amendment. All SAEs including AESIs reported as SAEs were captured in ARGUS safety database throughout the study.

Thorough manual review was implemented to ensure SAEs reported both in ARGUS and RDC databases were uniquely matched without any missing or overlapped inputs.

Hence, AEs/SAEs from both ARGUS safety database and RDC clinical database will be summarized separately to ensure comprehensive and transparent safety data reporting. Global protocol amendment date (18-Mar-2016) as a general cutoff date will be applied to analyze safety data from RDC clinical database.

The following AE summary tables will be provided:

I. from Safety Database (ARGUS):

- All SAEs throughout the study
  - SAEs regardless of study treatment relationship by primary system organ class and preferred term
  - SAEs suspected to be study treatment relationship by primary system organ class and preferred term

- All AESI reported as SAEs as per protocol throughout the study
  - Serious AESIs regardless of study treatment relationship by safety topic and preferred term

II. from Clinical Database (RDC):

- AEs (non-serious AE and AESI) after protocol amendment
  - AEs regardless of study treatment relationship
    - a. by primary system organ class, preferred term and maximum CTC grade
    - b. by primary system organ class and preferred term
  - AEs suspected to be study treatment related
    - a. by primary system organ class, preferred term and maximum CTC grade
    - b. by primary system organ class and preferred term
  - AEs leading to study drug discontinuation regardless of study drug relationship by primary system organ class and preferred term

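### 'Study treatment' has two meanings in the documents, so the suspected-related tables admit Sandostatin-only reactions and none isolates everolimus

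*SAP*

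**What the plan says.** The documents use the term in two ways.

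- **Everolimus only.** Protocol 6.1: "Study treatment and investigational treatment refer to everolimus".
- **Combination included.** The protocol glossary says of combinations that "study treatment in this case refers to the investigational and non-investigational treatments in combination". Protocol Table 6-2, in its study-treatments column, lists "Sandostatin LAR® (if applicable"). SAP 2.1.1 says that study treatment "is defined as everolimus or everolimus + Sandostatin LAR if patients are allowed to continue combination therapy".

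The SAP has a separate term, study drug, for everolimus alone: "RAD001 = everolimus = Afinitor".

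Causality is collected in two ways. For adverse events, protocol 8.1.1 asks one question: "Its relationship to the study treatment (reasonable possibility that AE is related: No, Yes"). For serious events, protocol 8.2.2 asks for the "relationship of each SAE to each specific study treatment (if there is more than one study treatment").

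SAP 2.8.2 then plans suspected-related tables for SAEs from ARGUS and for AEs, AESIs and SAEs from RDC. All are keyed to study treatment, for example "SAEs suspected to be study treatment relationship by primary system organ class and preferred term". SAP 2.8.1 plans exposure for both everolimus and everolimus + Sandostatin LAR, but SAP 2.8.2 does not split any event table by drug or regimen.

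**The concern.** Protocol 2.1 gives the purpose as characterising the long-term safety of everolimus. The study has one arm, so investigator attribution is the main causality information the report will contain. Protocol 10.5.3.2 names relation to study treatment as one of the dimensions for summarising AEs.

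Under the SAP definition, a combination patient's event qualifies as related if the investigator blames either drug. A reader of the report would probably take a related event to mean related to everolimus. For combination patients the planned tables do not support that reading, and nothing else in the table plan supplies it. The serious and non-serious tables may also rest on different definitions, because one causality record is per drug and the other is a single answer. SAP section 4 declares no change from the protocol, so the report would not alert the reader to any of this.

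**Working it through.** The plan states no figure on this point, so the check is mainly a comparison of the texts.

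**1. What the term covers**

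| Place | Meaning of study treatment |
|---|---|
| Protocol 6.1 | everolimus |
| Protocol glossary | all drugs in the combination |
| Protocol Table 6-2 | Sandostatin LAR is listed under it |
| Protocol 8.2.2 | may be more than one drug |
| SAP 2.1.1 | everolimus, or both drugs for combination patients |

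Protocol 6.1 stands alone; the SAP agrees with the other protocol passages.

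**2. Which tables depend on it**

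- Suspected-related tables (ARGUS SAEs; RDC AEs, AESIs and SAEs): yes, all use study treatment.
- Tables of events regardless of relationship: no. The count is the same under either meaning.
- RDC tables of events leading to discontinuation, to dose adjustment or interruption, or to additional therapy: these use study drug, so the SAP has the everolimus-only term available but does not use it for relatedness.

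**3. A Sandostatin-only reaction in a combination patient**

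- Serious event: the SAE report should show everolimus no, Sandostatin LAR yes. Under SAP 2.1.1 it enters the related SAE table. The information needed to separate it has been collected.
- Non-serious event: one Yes/No answer. If the item meant everolimus, the answer is no and the table counts correctly under a wrong label. If it meant the combination, the answer is yes and cannot be split afterwards. The CRF is not in the documents, so this cannot be settled here.
- Patient on everolimus alone: no effect under any definition.

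**4. Scale**

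- Patients, from SAP 2.1: 21 ongoing + 11 discontinued = 32 at the amendment; 32 + 2 enrolled later = 34.
- SAP 2.8.2 tables count patients, not events. One patient newly counted for a term adds 1/34 = 2.9 percentage points, assuming all 34 are in the Safety Set. A second event in the same patient for the same term adds nothing.
- If the RDC tables used only patients observed after the amendment (an assumption: 21 + 2 = 23), the step would be 1/23 = 4.3 points.
- SAP 2.1 says about 30% of enrolled patients had AEs in RDC: 0.30 × 34 ≈ 10. So the single AE item can matter for about 10 patients at most, and only for those among them on the combination.
- Combination patients: not stated, so no total can be computed.

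**The case against.** The strongest reply is that this is a wording slip in protocol 6.1 with little consequence. The SAP follows the glossary, Table 6-2 and 8.2.2. The protocol itself asks for a summary by relation to study treatment. SAE causality is recorded per drug, and SAP 2.1 promises listings of all data, so with 34 patients attribution can be read line by line. Events ongoing from the parent study go to medical history (protocol 8.1.1), so established reactions to continued octreotide enter only if they worsen.

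Much of this stands. A reader might infer that the SAP departs from a protocol that uniformly means everolimus; it does not, because the protocol contradicts itself. A reader might also infer that sites answered the AE question differently depending on which definition they followed; the documents do not show how any site answered.

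What does not fall away is the table plan. A listing lets a determined reader reconstruct everolimus attribution for SAEs, but the report's summary tables would still carry the mixed definition. For non-serious events even the listing may not resolve it.

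**Conclusion.** The inconsistency is real, and as written the suspected-related tables do not isolate everolimus. For SAEs the gap lies in the tables, not in collection. For RDC AEs it may lie in the collected item itself.

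The size is modest and not fully knowable: 2.9 points per combination patient newly counted for a term on a denominator of 34, an unknown number of such patients, and a total that may be zero.

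A reader might infer that Sandostatin reactions could be assigned to everolimus in the primary endpoint. The documents do not support that. Protocol Table 3-1 sets the endpoint as frequency and severity of all AEs and SAEs, whatever their cause, and those counts do not move. Nor can a share of combination patients be assumed in order to give a total, since neither document offers a basis for one. No hypothesis is tested, so no error rate is at stake. The consequence is interpretive: the related tables cannot be read as everolimus tables.

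**What to change.** 1. Use one definition of study treatment in protocol 6.1, the protocol glossary and SAP 2.1.1. The SAP's study drug already serves where everolimus alone is meant.
2. In SAP 2.8.2, report ARGUS SAEs, including AESIs reported as SAEs, that are suspected to be related to everolimus, using the drug-specific causality required by protocol 8.2.2. List separately those attributed only to Sandostatin LAR. The 8.2.2 wording is conditional on there being more than one study treatment, so confirm that the per-drug field was completed for combination patients.
3. For RDC events with the single Yes/No item, state which drug or drugs the item referred to. Show the suspected-related AE and AESI tables separately for patients on everolimus alone and on the combination, with the number in each group. The Sandostatin dosing eCRF (protocol 6.6.3.3) identifies the groups. State which causality record the RDC SAE table uses.

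Rewording the causality item in protocol 8.1.1 would help only future data; it cannot re-attribute AEs already collected. Regimen columns on every other table are optional in a study of 34.

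The cost is SAP text and a few extra tables. The downsides are small cells and possibly slightly lower related percentages.
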